## References

American College of Sports Medicine. (2021). *ACSM’s guidelines for exercise testing and prescription, eleventh edition*. Philadelphia: Wolters Kluwer.

Centers for Disease Control and Prevention. (2021, October 20). *Radiation and Your Health*. U.S. Department of Health and Human Services. Retrieved October 13, 2022 from [cdc.gov/nceh/radiation/dexa-scan.html](https://cdc.gov/nceh/radiation/dexa-scan.html)

Community Health Needs Assessment 2019. (2018). Peninsula Regional Medical Center and Wicomico and Somerset County Health Department.  
<https://somersethealth.org/wp-content/uploads/2017/03/community-health-needs-assessment-2019.pdf>

*Department of Kinesiology*

[REDACTED]

[REDACTED]

[REDACTED]

“The Implementation Of A Community Health-focused Intervention Using Combined Aerobic and Resistance Training Protocols In A Group Setting”

Date: February 21, 2023

Subject: Amendment to IRB Protocol #11-2022-004

---

This amendment requests the additional use of a Bod Pod to assist in analyzing body composition periodically, at the 8-week point and again at the 12-week point. The 8-week point would be the second week of March and the 12-week point would be the first week of April. The principal investigator (PI), myself, will operate the bod pod. The PI completed the 2-hour training session with the representative from COSMED, the Bod Pod manufacturer. The Bod Pod is in the new School of Pharmacy and Health Professions building in room 3114, on the campus of University of Maryland Eastern Shore, registered to the department of kinesiology room. The Bod Pod is a large egg-shaped device that uses air displacement to calculate body density (body mass/volume). The device predicts body fat percent and fat free mass from various body density equations depending on the subject’s race or ethnicity, age, gender, and predicted thoracic gas volume. The thoracic gas volume may be predicted and determined by the device, or it may be completed manually. This protocol will have the Bod Pod device predict and determine thoracic gas volume while the subject is sitting inside the Bod Pod.

To increase the accuracy of the Bod Pod, subjects must wear tight-fitted clothing such as spandex/tights or single-layer compression shorts and a sports bra or camisole for females. The subject’s hair is also secured under a tight-fitted cap supplied by the department of kinesiology. The department will supply each participant their own plastic shower cap to put between their hair and the required tight-fitted cap that comes with the Bod Pod. Jewelry is not allowed to be worn and cell phones cannot be taken inside the chamber. Socks may not be worn either. The subject’s body weight is measured by a scale that is calibrated for use with the Bod Pod. The subject will be asked to stand on the scale and then step off the scale once body weight has been determined. The body weight will automatically be loaded to the software program on the connected computer. The software program is called Omnia which is where all the information collected will be stored. The computer that includes this software program is

username and password protected. Five individuals, including myself, know the username and password to log on to the computer to access the software. The individuals who know the log in information work in the department of kinesiology. The computer is attached to the Bod Pod and therefore, it cannot be removed from the room. The room is locked at all times. The administrative assistant in the office of the dean and, potentially, the campus police are the only individuals who have access to the room. Neither know the username nor password for the computer.

After stepping off the scale, the subject would then be asked to step in and sit in the Bod Pod chamber which includes a large glass window for the participant to look out of. The subject will be instructed to sit and remain still as possible while the analysis is taking place. The Bod Pod door will be closed and opened following on-screen prompts. The door will be opened twice in timed intervals while the subject remains seated and still as possible. The door opening and closing allows the Bod Pod device to calculate consistent readings in terms of the air that has been displaced by the subject sitting inside the chamber. The subject will be told that the entire process takes about three minutes, if there are no interruptions or errors with the device causing a repeat of the steps, including all the intervals with the door opening and closing. Once the on-screen prompt says the analysis is complete, the PI will open the door and allow the subject to put any additional clothing back on. The results will then be shared with the subject. The results may also be printed out for the subject and the PI to receive a copy. Individual subject data from the analysis will be identified on the software program as colors. The PI will have a key for these colors. The key will identify which color goes with which subject's middle name. The subject's middle name was initially used during the first week of the pre-assessment and preliminary fitness test. A color is now being used as a second layer since four other departmental members have access to the Bod Pod device and software program. The PI will not share the colors with anyone. The key for the colors and the Bod Pod analysis will be kept in the locked cabinet where the signed informed consents are.

Contraindications associated with the addition of this body composition device include claustrophobia. In addition to this, subjects may be self-conscious or uncomfortable with wearing tight-fitted, spandex shorts and a sports bra or camisole. Other risks include emotional discomfort as a result of seeing the analysis results related to their body composition. To minimize risk associated with claustrophobia, subjects will be allowed to complete a practice analysis of which they will be allowed to remain fully dressed. If during or after the practice analysis, the subject chooses not to complete the Bod Pod assessment, the subject is free to leave the room but may continue with the intervention without this assessment. If after the practice analysis the subject desires to run through the real analysis but then midway through decides they do not want to, the PI may click the 'abort' button to stop the analysis to allow the subject to come out of the chamber. On the inside of the chamber, the subject also has the ability to stop the test as well. The subject would be informed that they may press the 'blue' button which is on the chamber seat. The chamber is not locked however the PI must open the door. To minimize the discomfort with the required attire, a large sheet will be placed over the room's front window. In addition, the subject may choose not to complete the Bod Pod analysis at all. The accuracy of the analysis requires tight-fitted clothing such as spandex and

this will be explained during the (updated) informed consent process. Lastly, to minimize emotional discomfort associated with seeing the results from the analysis, the subject will receive positive reinforcement and encouragement as having made it to the 8-week and/or 12-week point. The PI will emphasize to the subject that they should view the results as a motivational tool only.

To increase the accuracy of the Bod Pod analysis, subjects should restrict their eating and exercise up to two hours before the assessment takes place. As a result, all the subjects will be tested on a non-intervention (exercise) session day of their choice. Subjects may be hungry since they would not have eaten for two hours and therefore, the PI will have a supply of snacks in the room for the subject after the assessment. Snacks will include the normal post-intervention snacks that the subjects are already familiar with. These snacks include dried fruit, nuts, and protein bars.

Since jewelry cannot be worn, the subject will be asked to place their jewelry in a safe place with the other belongings that he/she has brought to the analysis session. Since the subject may be uncomfortable with this, the PI will re-emphasize that the analysis is about three total minutes, if there are no interruptions or errors with the device causing a repeat of the steps, and they are free to put the jewelry back on as soon as the chamber door opens back up at the conclusion of the analysis. Since a cellphone cannot be taken inside the chamber, the participant will be asked to place their cellphone in a safe place and/or in a place that is comfortable for him/her. When the chamber door opens at the end of the analysis, the PI will allow the subject an opportunity to get their jewelry and cellphone prior to any discussions about the analysis if that is what the subject desires to do. Socks may also not be worn during the analysis and therefore the PI will clean the floor on the inside of the chamber with a Clorox wipe while in the presence of the subject. On the contrary, the subject will be allowed to wear their socks while they are on the body weight scale. The restriction of jewelry, cellphones, and socks may also present risks for the subject that include a lack of comfort related to losing or forgetting something that is valuable. The PI will allow the subject to take off or put away all items right before entering the chamber and the PI will allow the subject to return and get all items right after the analysis is complete and the chamber door opens. The PI will wipe the floor in the chamber with a Clorox wipe and dry it with a paper towel so that the participant can see the floor has been sanitized.

Benefits associated with the addition of this body composition device have to do with its level of accuracy comparable to bioelectrical impedance analysis devices. Measuring body density is used as a criterion standard for assessing body composition. Underwater weighing and DEXA have since been considered the criterion measure. However, use of the Bod Pod reduces the challenges/risks associated with being submerged in water and/or being exposed to radiation (ACSM, 2021). The inclusion of the Bod Pod allows the body composition results to be more reliable.

American College of Sports Medicine. (2022). *ACSM's guidelines for exercise testing and prescription 11th edition*. Philadelphia: Wolters Kluwer.

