Title: The implementation of a community-health focused intervention using combined aerobic and resistance training protocols in a group setting.

NCT number (not available)

February, 23, 2023

Title: The Implementation Of A Community Health-focused Intervention Using Combined Aerobic and Resistance Training Protocols In A Group Setting

1. Research Design/Methods

- a. The purpose of this project is to provide an intervention focused on a combination of aerobic and resistance training exercise for adults residing in Somerset County, Maryland. Through a pre-determined, structured exercise program, participants will engage in physical activity sessions for 12 weeks. The program will be offered from January 9-March 31, 2022. This approach is appropriate as Somerset County has the highest physical inactivity level and poorest physical health amongst surrounding counties (CHNA, 2019). Currently, Somerset County residents only have access to fitness classes, offered twice a week, which take place in a classroom at Somerset Technical High School. The class is offered through Somerset County Recreation, Parks, and Tourism and interested participants pay a fee to join. However, this project offers participants pre and post assessments and monitored aerobic and resistance training sessions with a primary outcome of improving body weight, body composition and/or measures of fitness.

2. Subject Selection

- a. The subjects are adults, 18 years or older, residing in Somerset County. There is not an upper age limit to participate in the program. Funding for this project requires activities that address the poor health outcomes of adults in Somerset County, Maryland. Somerset County Health Department will assist in advertising for the project as the intervention is open to adults, 18 years of age or older, in Somerset County.
- b. Flyers will be posted around Somerset County. Somerset County Parks & Recreation will be contacted and sent a flyer. The flyer is attached.
- c. Subjects will be recruited from Somerset County, Maryland. This is a requirement for the funding that was received for the project. The PI will ask surrounding businesses and organizations permission to post the project flyer.

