An ACSM screening algorithm and the PARQ+ will be used to determine if a participant needs medical clearance prior to participation in the preliminary fitness tests which is completed a week before the program begins. The preliminary fitness tests will include the curl up, the pushup, bench press, vertical jump, and the Rockport 1-mile or 1.5 mile walk test. The purpose of the fitness test is to acquire baseline data about physical fitness levels before implementation of the intervention. The preliminary fitness test will not be used to determine if an individual can or cannot participate. Participants will complete a Bio-electrical Impedance Analysis (BIA), body weight, and waist circumference measurements before and after the study. The BIA will be used to determine percent body fat, skeletal muscle, and body mass index. The PI will program the BIA device. The participant will be asked to step on a scale and hold the handle of the BIA device. The participant will be asked to hold the BIA device for up to 5 seconds until the device completes the scan. The weight of the BIA device is approximately 12 ounces. BIA devices are available for the public and may be purchased by the public. To measure the participant’s waist circumference, a tape measure will be placed around the participant’s waist on the outside of their shirt. The participant will be asked to identify where their belly button is and the participant will wrap the tape measure around their waist. One inch below the participant’s belly button is where the participant will be asked to place the tape measure. The BIA and waist circumference measurements will be conducted in the exercise science lab located in the Department of Kinesiology in Hytche Athletic Complex on UMES campus.

These data collected from participants will be recorded and stored on a password protected university-owned laptop. The participant’s middle name will be used as an

identifier until post assessments are complete. Post assessments are completed at the end of the program and will include all of the preliminary assessments.

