- b. Interested participants may call, email, or access the google form through the link provided by the principal investigator on the invitation to participate. Once the participant expresses interest by providing their contact information, an individual appointment will be scheduled to explain the study and the procedures. The informed consent, ACSM screening algorithm, PARQ+, and supplemental informed consents, if applicable, will be explained to the participant. The participant will be given time to ask questions. If the participant is still interested in participating, he/she will be asked to sign the documents. At these individual meetings, each participant will be provided a copy of the informed consent for him/her to keep.
- c. The readability report for the informed consent was over 12th grade with an age of 19 to 20 years old.

7. Research Plan for Collection, Storage, and Analysis of Data

- a. Data will be collected using a tape measure and a bioelectrical impedance analysis (BIA) device. Participants will be asked to complete a fitness test which includes a bench press, vertical jump, pushup, curl up, and either a 1-mile walk or 1.5 run/walk test. Data collected is what the participant completes through counting or by using a stopwatch. Participants can choose not to complete some or all of the fitness test. The PI is responsible for supervising all sessions. The PI is certified through both national certifying organizations, the National Strength and Conditioning Association and the American College of Sports Medicine, for exercise program design, implementation, and safety. The PI is required to maintain three certifications through pre-approved continuing education through the certifying organization as well as maintaining a current Cardiopulmonary Resuscitation (CPR) and Automated External Defibrillator (AED) certification. Additionally, there is a licensed athletic trainer working in Hytche Athletic Complex.
- b. Data will be stored in an excel spreadsheet on a password-protected laptop loaned to the principal investigator from the university. The PI is the only individual who has access to the laptop.

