- c. Data will be analyzed for the mean and standard deviation of pre and post individual assessment data as a result of the intervention sessions. ANOVA with significance set at  $p<0.05$  will be used to determine the significance of the change in body weight, composition, waist circumference, and measures of fitness that may or may not have occurred. The mean and standard deviation of scores, pre and post, will be calculated and reported.
- d. The PI is the only individual who will have access to the data. Participants may request a copy of personal measurements/assessments prior to the conclusion of the study as pseudonyms may be replaced with numbers.
- e. The data will be kept for three years at the conclusion of the study.
- f. After the three-year period, the file will be deleted from the computer and the deleted folder will be emptied.

8. Conflict of Interest

- a. Potential conflict of interest includes receiving a grant from Somerset County Health Department (SCHD) for the development and implementation of a health intervention program for adults in Somerset County. This research effort and collection of data is not a condition of the funding received. This project may be carried out without intentions of a publication and/or presentation however, it has the potential to contribute to a body of knowledge on community health interventions and how they may be implemented. Additionally, results obtained from this project will be useful in applying for additional funding opportunities that will benefit the surrounding community. A narrative will be shared with SCHD at the completion of the project however, no raw data will be shared. The narrative will include results from the data analysis. The funding covers the equipment that will be needed, supplies for the participants, and salary. Equipment will include items such as the most accurate BIA home device, medicine/physio balls, exercise mats, stretching bands, and dumbbells. Supplies will include items such as hand towels, water, sanitizing wipes, and post-session snacks. Salary will be given to the PI for development and implementation of the intervention. This conflict will not affect the level of risk to the study participants and will be disclosed in the informed consent. Additionally, disclosure of this conflict of interest will be included in publications and/or presentations of the study results.

9. HIPPA Compliance

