- a. This research includes the collection of protected health information. The participant's anthropometrics (body weight and waist circumference) and body composition (BIA) will be recorded at the beginning and again at the conclusion of the 12 weeks. The PI, however, will not be contacting health care providers for any reason. Participants are allowed to receive a copy of personal measurements and/or assessments to give to their physician if it is requested prior to the conclusion of the study. Pseudonyms will be replaced with numbers therefore it will be impossible to determine a specific individual's results at the conclusion of the study. The health screening will be an interview with the potential subject. The interview includes three questions to determine if medical clearance is needed prior to participation as a precautionary measure. The answers to

these questions will not be shared with anyone. The questions for the ACSM preparticipation screening include:

1. Do you participate in regular exercise?
2. Has a physician or other qualified health care provider ever diagnosed you with cardiac, peripheral vascular, cerebrovascular disease, or Type 1 or 2 diabetes?
3. Do you have any signs or symptoms suggestive of cardiovascular, renal, or metabolic disease including but not limited to: pain/discomfort in the chest, neck, jaw, or arms; shortness of breath at rest or with mild exertion; dizziness during exercise, ankle edema, palpitations (awareness of rapid beating of the heart) or tachycardia; or unusual fatigue or shortness of breath with usual activities?

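### Do Bod Pod readings at weeks 8 and 12, without a baseline reading, weaken the pre/post body composition result?

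*Combined protocol and SAP*

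**What the plan says.** Section 3a sets the body composition measurement at both ends of the programme: "Participants will complete a Bio-electrical Impedance Analysis (BIA), body weight, and waist circumference measurements before and after the study". It adds that the post assessments repeat all the preliminary ones. Section 9a agrees: "body composition (BIA) will be recorded at the beginning and again at the conclusion of the 12 weeks". Section 7a names the instruments: "Data will be collected using a tape measure and a bioelectrical impedance analysis (BIA) device". Section 7c gives the analysis: "Data will be analyzed for the mean and standard deviation of pre and post individual assessment data", followed by ANOVA at p<0.05 for change in weight, composition, waist circumference and fitness. It mentions neither an 8-week value nor the Bod Pod.

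The amendment adds the Bod Pod for "analyzing body composition periodically, at the 8-week point and again at the 12-week point" and dates the readings: "The 8-week point would be the second week of March and the 12-week point would be the first week of April". It refers to the pre-assessment as something already done. Its last paragraph gives the benefit: "The inclusion of the Bod Pod allows the body composition results to be more reliable". Its risk paragraph makes the reading optional and tells participants to treat the results purely as motivation.

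**The concern.** The only body composition comparison that the plan analyses is before against after. A device with no before value cannot contribute to it, and none can now be obtained for this cohort. The stated benefit therefore seems not to fit the schedule, although it is set against real burdens: possible claustrophobia, fitted clothing, two hours without food, and a visit on a non-session day.

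Two further risks suggest themselves. At week 12 both devices give a value, and Section 7c does not name the device, so an analyst might set a Bod Pod value against a BIA baseline. Or the change between the two Bod Pod readings might be tested. That interval holds few sessions, so a null result could be read as contradicting BIA.

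**Working it through.** **1. Can the Bod Pod improve the baseline-to-week-12 change?** Let m0, m8 and m12 be the true mean body composition at baseline, week 8 and week 12, and let d be the mean offset between Bod Pod and BIA. The four observed means estimate:

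- BIA at baseline: m0
- Bod Pod at week 8: m8 + d
- BIA at week 12: m12
- Bod Pod at week 12: m12 + d

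Four means determine four unknowns exactly. The estimate of m12 − m0 is therefore BIA at week 12 minus BIA at baseline, whatever the Bod Pod shows. Its standard error is √[(S² + 2E²)/n], where S is the SD of true change and E the BIA measurement SD. The documents give neither, so three assumed sets are used, in percentage points of body fat, with n = 15 (the cap in Section 2d):

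| S | E (BIA) | Bod Pod measurement SD | SE, BIA alone | SE with Bod Pod, d unknown | SE with Bod Pod, d = 0 |
|---|---|---|---|---|---|
| 2 | 1.5 | 1.5 | √(8.5/15) = 0.753 | 0.753 | 0.701 |
| 2 | 2.5 | 1 | √(16.5/15) = 1.049 | 1.049 | 0.861 |
| 1 | 3 | 1 | √(19/15) = 1.126 | 1.126 | 0.852 |

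The last column also assumes a between-person SD of 8 and two thirds of the change by week 8. A gain needs a zero offset, which the documents do not support. So the Bod Pod gives no gain for the pre/post change, and also no loss.

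**2. Does the plan mix devices?** Sections 3a and 9a put BIA at both ends, and Section 7a lists BIA as the body composition instrument. A Bod Pod pre/post change cannot be computed, because there is no pre value. No sentence sets a Bod Pod value against baseline BIA. The same holds for weight: the Bod Pod has its own scale, but Section 3a already repeats the preliminary weight measurement at the end.

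**3. Are the time labels wrong?** January 9 plus 56 days is March 6, and plus 84 days is April 3, in both 2022 and 2023. Eight and twelve completed weeks thus fit the second week of March and the first week of April. The printed year ("The program will be offered from January 9-March 31, 2022") does not fit an amendment of February 2023 written during the programme. It is a clerical slip and does not affect this count.

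**4. How much programme lies between the readings?** Section 3a gives one session a week for 2 weeks, then two a week: 2×1 + 10×2 = 22. With the first reading in the week of March 6, 6 to 8 sessions remain (6/22 = 27%, 8/22 = 36%). Later readings of the second week of March leave as few as 4 (18%).

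**5. What power would a week 8 to week 12 test have?** Assume n = 15 complete pairs, a two-sided paired t-test at 0.05, an effect that builds evenly by session, and a full-programme effect of 0.778 SD of paired differences (80% power pre/post). The window effect is 0.778 × 0.273 = 0.21 to 0.778 × 0.364 = 0.28 SD, and power is 12% to 18%. If the Bod Pod SD of differences is half as large, power is 33% to 53%. With a full effect of 1.5 SD instead, power is 31% to 50%, or 84% to 98% with the halved SD. The figure depends almost wholly on what is assumed, and it describes a test that no section plans.

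**The case for a change.** The strongest case for acting is that pre and post are the only results the plan defines, so the benefit sentence can only refer to them, and in that sense it is unsupported. A benefit set against burdens in an amendment ought to be one that the schedule can deliver. Section 7c also leaves the device unnamed, while the results go to the funder and may support further grant applications.

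Part of this stands. If the sentence is meant to cover the pre/post change, it claims too much. But it does not say pre/post. The same amendment describes periodic readings that are shown to the participant as motivation, and on that reading the sentence concerns the individual values at weeks 8 and 12. The Bod Pod can supply those, along with a late-programme change and a check of agreement with BIA at week 12. The sentence is also a rationale, and no analysis depends on it. The unnamed device in Section 7c is settled by Sections 3a and 9a. The burden is softened by the option to decline, the practice run and the means to stop the test. How the updated consent words the benefit cannot be judged, because those pages are not in the public document.

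**Conclusion.** No change follows. The fact behind the concern is right: without a baseline reading the Bod Pod adds nothing to the baseline-to-week-12 change unless the two devices are assumed to agree on average. But that change rests on BIA at both ends, the amendment leaves it intact, and its estimate and standard error are the same with or without the Bod Pod data. Naming BIA again in Section 7c would record what Sections 3a and 9a already say, and narrowing the benefit sentence would alter no result. The missing baseline cannot be recovered for this cohort, and no later cohort is planned.

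The algebra in step 1 needs only an unknown mean offset between devices; the SDs in the table are illustrative. The conclusion also assumes that the analyst keeps to one device within a change score, which is the ordinary reading of the plan. The session fraction and the power figures do not bear on it.

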#### 4. Risks & Anticipated Benefit Analysis

- a. Risks associated with participation in this study will include low to moderate cardiovascular and/or muscular fatigue, also known as delayed onset muscular soreness (DOMS), associated with a new mode of activity/bodily movements that may or may not be a part of the participant's normal routine. Aerobic and resistance training will result in an increase in heart rate which may be uncomfortable for participants. Additionally, resistance training may cause an increase in heart rate and blood pressure as a result of low to moderate exertion. Cardiovascular and/or muscular fatigue and DOMS are normal for adults to experience at the start of physical activity. It is also normal for DOMS to occur with adults who have a history of being physically active. Risks associated with a vertical jump include knee discomfort. To minimize knee discomfort, the participant will complete the assessment on an exercise mat which will soften the impact when landing. The participant is also permitted to complete one jump or no jumps at all, if applicable.

BIA is free of radiation and there are no known associated risks with this. The participant, however, may experience emotional discomfort from his/her body weight, body fat, and/or waist being measured. The PI will provide encouragement to the participant and remind them of the purpose of the research study. The PI will also ask the participant if he/she would rather not know their individual measurements. Lastly, the participant will be reminded that he/she may withdrawal from the research study at any time.

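### The Bod Pod amendment does not carry over Section 4a's choice not to know one's measurements: anyone who completes the test is told the result

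*Combined protocol and SAP*

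**What the plan says.** **Base protocol.** Section 4a (Risks & Anticipated Benefit Analysis) says that the participant "may experience emotional discomfort from his/her body weight, body fat, and/or waist being measured". It lists several protections: encouragement, a reminder of the study's purpose, a reminder that withdrawal is possible, and this question: "The PI will also ask the participant if he/she would rather not know their individual measurements". Elsewhere results are available by choice. Section 5a allows participants to be given their own results, Section 5b has the PI ask each person whether they want a copy, and Sections 7d and 9a allow a copy on request before the study concludes.

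**Amendment to IRB Protocol #11-2022-004 (Bod Pod).** The procedure ends with a flat statement: "The results will then be shared with the subject". A printout is optional. On risk, it says: "Other risks include emotional discomfort as a result of seeing the analysis results related to their body composition". The response is: "Lastly, to minimize emotional discomfort associated with seeing the results from the analysis, the subject will receive positive reinforcement and encouragement". It adds: "The PI will emphasize to the subject that they should view the results as a motivational tool only". The test itself is voluntary: "In addition, the subject may choose not to complete the Bod Pod analysis at all". A subject may also leave after a practice run or stop the test midway, and may continue the program without it. On timing: "The 8-week point would be the second week of March and the 12-week point would be the first week of April".

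**The concern.** The base protocol lets a person be measured without being told the number. The amendment, followed literally, does not. Its risk is defined as distress from seeing the result, so the most direct protection would be the option not to see it, and that is the one Section 4a protection aimed at exactly this. A PI holding both texts has no clear instruction for a participant who earlier said they would rather not know their body fat.

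What is at stake is mainly participant protection and consistent conduct. A lesser matter is interpretation: week-8 results reach participants while the program is still running, so any response to them forms part of the pre-post change.

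**Working it through.** The documents give no statistical figure on this point. The check is a comparison of text plus simple date and session counts.

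**1. Do the two texts cover the same quantities?** Section 4a names body weight, body fat and waist. The Bod Pod procedure records body weight on its own scale and predicts body fat percent. Two of the three quantities overlap.

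**2. Side by side.**

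| | Section 4a | Bod Pod amendment |
|---|---|---|
| Risk named | Discomfort from being measured | Discomfort from seeing the results |
| Encouragement | Yes | Yes |
| Asked whether they would rather not know | Yes | Not mentioned |
| Result given | By choice | Stated without condition once the test is complete |
| Way to avoid the result | Say so when asked, and still be measured | Decline or abort the test |

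The amendment neither repeats the Section 4a question nor withdraws it. For a participant who does not want to know, the two texts point in opposite directions.

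**3. How many people?** Section 2d caps the project at 15. With tests at the 8-week and 12-week points, the upper bound is 15 × 2 = 30 disclosures. The actual number depends on uptake, which is unknown.

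**4. Timing.** Section 1a gives January 9 to March 31. January 9 plus 8 × 7 = 56 days is March 6, the start of week 9 in a non-leap year. From March 6 to March 31 is 25 days, or 25/7 ≈ 3.6 weeks. If the second week of March is read as running to about March 17, 14 days (2 weeks) remain. So week-8 results arrive roughly 2 to 4 weeks before the program ends, and Section 3a places the post assessment at the end.

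**5. Sessions left.** Section 3a moves from one to two sessions a week after two weeks: 2 × 1 + 10 × 2 = 22 sessions. A test in week 9 leaves 3 × 2 = 6 sessions, plus up to 2 in that week (6 to 8). A test in week 10 leaves 2 × 2 = 4, plus up to 2 (4 to 6). The range is therefore 4 to 8 of 22.

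**6. What happens to the analysis if someone declines the Bod Pod?** Its first use is at week 8, so it has no baseline. Section 7c analyses pre and post values, and Section 3a takes weight, BIA and waist before and after the study. A declined Bod Pod test removes none of these.

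**7. Can exposure to feedback be identified?** Under the amendment as written, completing the test means being told. Completed tests are stored in the device's software under color codes with a key, so who received week-8 results can be recovered.

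**The case against.** The strongest reply is that the amendment requests an additional device and cancels nothing. Section 4a refers to individual measurements generally, so its question can be read as still applying. A reader might infer that the safeguard has been removed; the text does not support that. It supports only that the safeguard is not carried over. The reply does not remove the problem, because the amendment's disclosure sentence has no exception and its own list of mitigations leaves the question out. The updated consent mentioned in the amendment is not available for this review, so it may offer the choice. That cannot be counted either way, and the procedure text would still need to match.

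Several stronger readings also fail:

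- **Everyone is told.** No. Only those who complete a voluntary test are told.
- **Feedback before the post assessment is new.** Not wholly. Sections 5, 7d and 9a already give participants access to their results. What is new is a mid-program measurement with disclosure as the default.
- **The amendment sets out to change behavior.** The motivational wording follows directly on the aim of reducing discomfort. It is a way of softening results. The amendment's stated purpose is to help analyze body composition.
- **The pre-post comparison is biased.** There is one group and no between-arm contrast to distort. Feedback cannot be separated from the sessions, but assessments and access to results were already part of the project. The documents give no basis for sizing any effect.
- **Declining costs outcome data.** It loses a Bod Pod reading but nothing from the planned weight, BIA and waist analysis.

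**Conclusion.** The point holds as a conflict between two stated rules. Section 4a offers the choice not to know. The amendment, for the same kind of risk and overlapping measurements, states disclosure without condition and answers the risk with encouragement. Anyone who completes the test is told, and avoiding the result means forgoing the test.

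Its reach is at most 15 people and 30 disclosures. It is a participant-protection and consistency issue, cheap to correct, and not a threat to the planned analysis. The conclusion assumes that staff would follow the amendment's procedure as written and that the updated consent does not already settle the matter.

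A reader might go further and ask that week-8 results be held until the post assessment. The documents do not support requiring this: it would cut against the access to results that the protocol promises, with no control arm to protect and no effect that can be sized.

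**What to change.** Reconcile the two texts. Replace the unconditional disclosure sentence in the amendment with wording such as: *Before each Bod Pod test, the PI will ask whether the participant would like to know the result. Results will be shown or printed only for participants who say yes.* Put the same statement in the updated consent, and cross-refer to Section 4a so that one rule covers all body measurements.

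Once disclosure is optional, completing the test no longer shows who was told. If the investigator wants to keep that information, a yes/no entry at the 8-week test is enough, with a sentence in the report that week-8 feedback is part of what the pre-post change reflects.

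The cost is one or two sentences in each document, one question per test and, optionally, one extra data column. Participants who want their results still get them at once, and those who do not can still be measured.
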